10.1.1 Complete remission (CR)

CR requires all of the following criteria present at one time point and still present when re-assessed at least 2 months after initial documentation:

- **Peripheral blood lymphocytes (evaluated by blood and differential count) below $4 \times 10^9/L$ (4000/ μL).**
- **Absence of significant lymphadenopathy (eg, lymph nodes >1.5 cm in diameter) by physical examination.** A CT scan of the chest, abdomen, pelvis will be used to confirm complete response if previously abnormal, and on that CT, lymph nodes should not be larger than 1.5 cm in long axis diameter.
- **No hepatomegaly or splenomegaly by physical examination.**
- **Absence of constitutional symptoms.**
- **Blood counts above the following values:**
 - Neutrophils more than 1500/ μL without need for exogenous growth factors.
 - Platelets more than 100 000/ μL without need for exogenous growth factors.
 - Hemoglobin more than 11.0 g/dL without red blood cell transfusion or need for exogenous erythropoietin.
- **For patients on this study meeting the above criteria for CR, a marrow aspirate and biopsy must confirm CR.** To define a CR, the marrow sample must be at least normocellular for age, with less than 30% of nucleated cells being lymphocytes. Lymphoid nodules should be absent. In some cases, lymphoid nodules can be found, which often reflect residual disease.^{55,56} These nodules should be recorded as “nodular PR.” Moreover, immunohistochemistry should be performed to define whether these nodules are composed primarily of T cells or lymphocytes other than CLL cells or of CLL cells. If the marrow is hypocellular, a repeat determination should be performed after 4 weeks, or not until peripheral blood counts have recovered. However, this time

CONFIDENTIAL

This document is confidential. Do not disclose or use except as authorized.

interval should not exceed 6 months after the last treatment. A marrow biopsy should be compared with that of pretreatment marrow and the quality of the CR should be assessed for MRD by flow cytometry.

Patients who fulfill all the criteria for a CR (including the marrow examinations described above) but who have a persistent anemia or thrombocytopenia or neutropenia apparently unrelated to CLL but related to drug toxicity will be considered CR with incomplete marrow recovery (CRi). For the definition of this category, CRi, the marrow evaluation should be performed with scrutiny and not show any clonal infiltrate.

10.1.2 Partial remission (PR)

PR is defined by the criteria described below if abnormal before therapy, as well as one or more of the blood count requirements. To define a PR, these parameters need to be documented for a minimal duration of 2 months.

- **A decrease in the number of blood lymphocytes by 50% or more from the value before therapy.**
- **Reduction in lymphadenopathy (by CT scans or by physical exam) as defined by the following:** (1) A decrease in lymph node size by 50% or more either in the sum of the bidimensional products of up to 6 lymph nodes, or in the largest diameter of the enlarged lymph node(s) detected prior to therapy AND (2) No increase in any lymph node, and no new enlarged lymph node. In small lymph nodes (< 2 cm), an increase of less than 25% is not considered to be significant.
- **A reduction in the noted pretreatment enlargement of the spleen or liver by 50% or more on physical examination.**
- **The blood count should show one of the following results:** (1) Neutrophils more than $1.5 \times 10^9/L$ (1500/ μ L) without need for exogenous growth factors. (2) Platelet counts greater than $100 \times 10^9/L$ (100 000/ μ L) or 50% improvement over baseline without need for exogenous growth factors. (3) Hemoglobin greater than 110 g/L (11.0 g/dL) or 50% improvement over baseline without requiring red blood cell transfusions or exogenous erythropoietin.

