1.3 Secondary Objectives

To determine the CR rate and PFS of ofatumumab and idelalisib.

To determine the ORR, CR rate and rate of nodal PR with lymphocytosis for idelalisib given alone for two months of therapy to previously untreated participants

To determine the rate of lymphocytosis with idelalisib in previously untreated participants

To assess the safety of idelalisib in untreated participants and in combination with ofatumumab.

To determine whether clinical response correlates with known CLL molecular prognostic factors including FISH, *IGHV*, *ZAP-70*.

CONFIDENTIAL

This document is confidential. Do not disclose or use except as authorized.

To determine whether the use of CT scans in response assessment improves the predictive power of ORR for progression-free survival or time to next treatment.

To determine whether serum ofatumumab and/or idelalisib levels in vivo predict response.

To assess whether initial treatment with idelalisib alters the cell surface marker phenotype of circulating CLL cells.

To assess whether in vivo treatment with idelalisib alters CLL cell sensitivity to therapy with antibodies or other kinase inhibitors.

To assess pharmacodynamic markers of PI3 kinase inhibition including AKT phosphorylation, production of T cell chemokines and response to CXCR 4/5.

To determine whether response or resistance correlates with genetic alterations in PIK3CA or PIK3CD or other genes.

To determine the influence of idelalisib treatment on intrinsic innate immune suppression and on regulatory T cells.

To identify predictors of response and resistance to idelalisib through biochemical and genetic analysis of the PI3K pathway.

To assess the clonal dynamics of CLL in peripheral blood vs bone marrow, and during therapy with idelalisib.

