5. TREATMENT PLAN

Treatment will be administered on an outpatient basis. Expected toxicities and potential risks as well as dose modifications for ofatumumab are described in Section 6 (Expected Toxicities and Dosing Delays/Dose Modification). No investigational or commercial agents or therapies other than those described below may be administered with the intent to treat the participant's malignancy.

Idelalisib lead-in followed by ofatumumab 8 wks later

All therapy with idelalisib has been discontinued. Patients on drug stopped as of 3/11/16. Those currently receiving ofatumumab may complete the planned course and evaluations as below. Those who have not yet reached day 57 may initiate ofatumumab at present. On day 57, ofatumumab will begin with the 300 mg dose. Ofatumumab will then be administered at 1000 mg weekly to complete 8 weeks (days 64, 71, 78, 85, 92, 99, 106) throughout Cycles 3 and 4. Cycle 4 will last 49 days (7 weeks) to accommodate the Ofatumumab dosing schedule. This will be followed by monthly ofatumumab on weeks 20, 24, 28, 32 to complete 4 additional cycles (5-8). The overall induction treatment period will then be up to 8 months, including whatever idelalisib was received prior to March 11, 2016. Restaging with CT scans will happen after Cycle 2, on cycle 4 day 22, and a final restage will occur 2 months after the completion of ofatumumab. There will be a tumor response assessment done via physical exam after Cycle 8.

Table 1: Treatment Description

Agent	Pre-medications; Precautions	Dose	Route	Schedule	Cycle Length
Idelalisib	None	150 mg BID	Oral	Discontinued	28 days (4 weeks) (Except cycle 4-49 days, 7 weeks)
Ofatumumab	Pre-medication before each ofatumumab infusion must be given within 30 minutes to 2 hours prior to the treatment: Acetaminophen 1000 mg po Benadryl 50 mg IV or po Methylprednisolone 50 mg IV*	300 mg at 0.3 mg/ml in NS; followed one week later by 1000 mg at 1 mg/ml in NS	IV after administration of Idelalisib and premeds	Weekly x 8 doses, then monthly x 4 doses	
* If the 2 nd infusion has been completed without the subject experiencing any grade = 3 AEs, pre-medication with glucocorticoid may be reduced or omitted before the 3 rd to N th infusion at the discretion of the investigator.					

CONFIDENTIAL

This document is confidential. Do not disclose or use except as authorized.

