9. STUDY CALENDAR

Screening evaluations are to be conducted within 14 days prior to start of protocol therapy. Scans and Bone Marrow Biopsies must be done ≤ 4 weeks prior to the start of therapy. In the event that the participant's condition is deteriorating, laboratory evaluations should be repeated within 48 hours prior to initiation of the next cycle of therapy.

All assessments must be performed prior to administration of any study medication. All study assessments and medications should be administered within ± 3 days of the protocol-specified date during the induction phase and ± 7 days of the protocol-specified date in the post-induction phase, unless otherwise noted.

Table 10

Procedures	Screen	Treatment Phase					Post Induction Phase		Long Term Follow-up	Survival Follow-up
		Cycle 1-2 Idelalisib only (Days 1-56)	Cycle 3 & 4 Weekly Ofa + Idelalisib ¹⁵	Cycle 5-8 Monthly Ofa + Idelalisib	Restage Cycle 4 day 22	Cycle 2 day 22 (Restage end of cycle 2), Cycle 10 day 1 (Final Restage 2 months after end of ofa therapy) and off treatment prior to cycle 10	Cycle 9 Day 1	Every 2 mos while on study drug beginning Cycle 10		
								Every 3 or 6 months ¹¹	Yearly	

CONFIDENTIAL

This document is confidential. Do not disclose or use except as authorized.

Informed Consent	X									
Demography	X									
Medical History	X									
Bone marrow biopsy	X ¹					X ¹		X ¹		
Flow Cytometry by Marrow or blood ¹⁶	X				X	X				
MRD on bone marrow						X				
CT (Chest Abdomen Pelvis)	X ²				X ²	X ²		X ²	X ²	
Tumor Assessment by PE	X				X	X	X	X	X	
CLL FISH panel (on bone marrow)	X					X (ON BONE MARROW)				
Banking at CRC, with Flow Cytometry ³	X	C1 DAY 8 & 15, C2 DAY 1	C3 D8 & 15, C4 D22			X				
DFCI Studies: Genomic Profiling ⁴	X							End of therapy ⁴		
Banking at Clinical Research Consortium for Sites participating in a CRC study ¹⁷	X									
Procedures	Screen	Treatment Phase					Post Induction Phase		Long Term Follow-up	Survival Follow-up
		Cycle 1-2 Idelalisib only (Days 1-56)	Cycle 3 & 4 Weekly Ofa + Idelalisib ¹⁵	Cycle 5-8 Monthly Ofa + Idelalisib	Restage Cycle 4 day 22	Cycle 2 day 22 (Restage end of cycle 2), Cycle 10 day 1 (Final Restage 2 months after end of ofa therapy) and off treatment prior to cycle 10	Cycle 9 Day 1	Every 2 mos while on study drug beginning Cycle 10	Every 3 or 6 months ¹¹	Yearly

CONFIDENTIAL

This document is confidential. Do not disclose or use except as authorized.

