1. Bone marrow biopsies are required at screening, cycle 2 day 22 (end of cycle 2 restaging) and cycle 10 day 1 (final restaging). Those patients in clinical CR at any bone marrow restaging should have 4 color MRD flow cytometry performed at the time of their bone marrow evaluation. Bone marrow biopsy can also be done at any subsequent point to confirm a suspected CR. In addition to standard clinical testing, 15 cc bone marrow aspirate will be obtained at each bone marrow biopsy, for flow cytometry immunophenotyping and comparison to PB, as well as studies at OSU and Mayo Clinic. These heparinized aspirate samples will be sent to the CRC for processing and storage. In cases where it is unsafe or not feasible to obtain the appropriate quantity of aspirate, the performing clinician should indicate this in his/her note.
2. CT scan required at screening, cycle 2 day 22 (end of cycle 2), cycle 4 day 22, and cycle 10 day 1 (final restaging). In subsequent follow-up only if clinically indicated at investigator discretion and when a patient comes off treatment due to disease progression or toxicity. A CT scan of the chest, abdomen, pelvis and any other known sites of disease should be completed. Any regions captured at screening such as the neck must be followed by CT throughout subject's participation. All CT scans will be centrally reviewed. These scans should be burned onto CD and sent via FedEx to the Project Manager at DFCI, ATTN: (Project Manager), [name], Boston, MA 02215. The scan will then be reviewed at the Tumor Imaging Metrics Core at DFCI.

CONFIDENTIAL

This document is confidential. Do not disclose or use except as authorized.

3. Two sodium heparinized tubes (green tops) at screening and at subsequent times. Sodium heparinized bone marrow aspirate (5-10 cc, green top) at screening and cycle 2 day 22 (end of cycle 2 restaging) and cycle 10 day 1 (final restaging).
 4. Four sodium heparinized tubes (green tops) and saliva. Sodium heparinized bone marrow aspirate (5-10 cc, green top). Patients who come off treatment for toxicity or progressive disease, four 10 cc sodium heparin (green top) tubes of peripheral blood. If a patient coming off treatment due to progressive disease or toxicity is undergoing a bone marrow biopsy, and does not have significant circulating disease, send sodium heparinized bone marrow aspirate (5-10 cc, green top)

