14.2 Analysis of Secondary Endpoints

Other Secondary Objectives:

- To determine the CR rate and PFS of ofatumumab and idelalisib.
- To determine the ORR, CR and rate of nodal PR with lymphocytosis for idelalisib given alone for 2 months.
- To assess the safety of ofatumumab and idelalisib in combination.
- To determine whether clinical response correlates with known CLL molecular prognostic factors.
- To determine whether the use of CT scans in response assessment improves the predictive power of ORR for progression-free or overall survival.
- To determine whether serum ofatumumab levels in vivo predict response.
- To assess whether idelalisib alters the flow cytometric phenotype of circulating CLL cells.
- To assess whether in vivo treatment with idelalisib alters CLL cell sensitivity to therapy with antibodies or other kinase inhibitors
- To assess pharmacodynamic markers of PI3 kinase inhibition including AKT phosphorylation, production of T cell chemokines and response to CXCR 4/5
- To determine whether response or resistance correlates with genetic alterations in PIK3CA or PIK3CD or other genes
 - To assess the clonal dynamics of CLL in peripheral blood vs bone marrow, and during therapy with idelalisib.

Secondary Analysis:

The CR rate of combination therapy, ORR rate, and rate of nodal PR with lymphocytosis for idelalisib given alone for 2 months will be summarized as numbers and percentages. The Kaplan Meier method will be used to estimate the median progression free survival. The number and percent of patients who experience toxicities on combination therapy after at least one dose of treatment will also be summarized. Associations of clinical response rate and known prognostic factors will be assessed using Fisher's exact test.

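### CR and PR must persist for 2 months, but ofatumumab starts 7 days after the lead-in restaging, so no idelalisib-alone CR or PR can meet the rule on the planned schedule

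*Combined protocol and SAP*

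**What the plan says.** **Duration rule.** For PR, section 10.1.2 states: "To define a PR, these parameters need to be documented for a minimal duration of 2 months". For CR, section 10.1.1 wants all criteria "still present when re-assessed at least 2 months after initial documentation". The idelalisib-specific changes in section 10 concern lymphocytosis only: isolated lymphocytosis is not progression (10.1), and nodal PR with lymphocytosis is a separate category with no stated duration (10.1.4).

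**Endpoint.** Section 1.3 lists the objective: "To determine the ORR, CR rate and rate of nodal PR with lymphocytosis for idelalisib given alone for two months of therapy". The analysis sentence in section 14.2 covers the ORR and the "rate of nodal PR with lymphocytosis for idelalisib given alone for 2 months will be summarized as numbers and percentages". The idelalisib-alone CR rate is an objective in both sections, but that analysis sentence names a CR rate only for combination therapy.

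**Schedule.** Idelalisib is given alone on days 1 to 56 (section 9, Table 10). Section 5 then says: "On day 57, ofatumumab will begin with the 300 mg dose". CT and marrow restaging in the lead-in is at cycle 2 day 22 (section 9, footnotes 1 and 2).

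**When response is called.** Section 1.1 places a response evaluation before ofatumumab. Section 8.2.3 sorts patients into stable disease versus PR, or PR with lymphocytosis, after two months of single-agent idelalisib.

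**The concern.** A response definition and the endpoint that uses it have to fit the same time window. Here the definition needs at least 2 months of persistence, while the single-agent period is 8 weeks in total with its only full restaging one week before the end. The analyst who computes the idelalisib-alone ORR has three options, and the plan does not choose between them:

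1. Require both assessments on idelalisib alone. No CR or PR can then qualify, and under section 10.1.5 a day-50 PR without progression falls back to stable disease, which the plan treats as nonresponse.
2. Accept persistence checked after ofatumumab has started. The rate then partly reflects the combination.
3. Call the response on day 50 alone. Sections 1.1 and 8.2.3 point this way, but sections 10.1.1 and 10.1.2 do not permit it.

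Enrollment stopped at 27 patients (section 14.1), so each reclassified patient moves the rate by 1/27 = 3.7 percentage points, and by more on any smaller denominator. Idelalisib has been discontinued for all patients, so the lead-in cannot be repeated. The choice should not be made after the results are seen.

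**Working it through.** **Inputs.** Cycles are 28 days, except cycle 4 at 49 days (section 5, Table 1). Ofatumumab is given on days 57, 64, 71, 78, 85, 92, 99 and 106 (section 5). Physical exam and hematology are weekly in cycles 1 and 2, and both are also scheduled on cycle 3 days 1, 8 and 15 (Table 10). Induction visits have a window of 3 days either way, and assessments precede dosing (section 9). For the arithmetic, 2 months is taken as 56 days, the shortest reasonable reading; calendar months are longer and make the misfit worse.

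**Reproducing the plan's own days.** Cycle 3 day 1 = 2 × 28 + 1 = day 57, which matches section 5. Cycle 4 day 22 = 3 × 28 + 22 = day 106, which matches the last weekly dose.

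**Lead-in restaging to ofatumumab.** Cycle 2 day 22 = 28 + 22 = day 50. The gap is 57 − 50 = 7 days, and at most 60 − 47 = 13 with both windows stretched.

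**Longest persistence on idelalisib alone, no hold.** The first weekly on-treatment visit is day 8 and the last pre-ofatumumab assessment is day 57 before dosing.
- Nominal: 57 − 8 = 49 days.
- Windows stretched: 60 − 5 = 55 days.

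Both are below 56. For CR the span is shorter: marrow confirmation is required, and the only required on-treatment marrow in the lead-in is on day 50, which leaves the 7-day gap above.

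**When 56 days is first reached.**

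| PR first documented | 56 days later | Ofatumumab infusions already given |
|---|---|---|
| Day 50 (restaging) | Day 106, cycle 4 day 22 | 7 (days 57 to 99) |
| Day 8 (exam and counts) | Day 64, cycle 3 day 8 | 1 (day 57) |

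The second row requires that a weekly exam with counts can document a PR. Section 10.1.2 lets nodes be judged by CT or by physical exam, but Table 10 lists a formal tumor assessment by exam only at restaging within the lead-in. Either way, the duration is completed after ofatumumab has begun.

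**CR.** After day 50 the next required marrow is at cycle 10 day 1. Cycle 5 day 1 = 85 + 49 = day 134; cycle 8 day 1 = 134 + 3 × 28 = day 218; cycle 10 day 1 = 218 + 56 = day 274. That is not a floor, because footnote 1 adds: "Bone marrow biopsy can also be done at any subsequent point to confirm a suspected CR".

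**The case against.** **Section 10.2 dates a response from first documentation.** On this argument, a PR met on day 50 and still present on day 106 is a response with onset on idelalisib alone, and the plan is merely silent on confirmation. It is right that onset is dated there. But section 10.2 measures duration for a response that already qualifies; it does not waive the persistence that sections 10.1.1 and 10.1.2 make part of qualifying.

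**Ofatumumab cannot create an idelalisib-alone responder.** This stands. Every PR criterion, including the 50% fall in blood lymphocytes, must already be met on day 50. A reader might infer from section 2.5, which says ofatumumab clears blood disease well, that the single-agent ORR would be inflated by new responders. The documents do not support that. The bias is narrower: ofatumumab could sustain a response that would have been lost on idelalisib alone.

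**Day 106 is not the earliest confirmation for every patient.** This also stands. It applies to a PR first documented on day 50; one documented on day 8 reaches 56 days on day 64.

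**Some supporting passages are thin.** Section 8.2.4 only labels a blood draw as the two-month restaging, and section 12.1.2 sets a general deadline for response forms. Neither shows that a final response is called on day 50, so the point rests on sections 1.1 and 8.2.3.

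**A drug hold pauses the assessment schedule (section 6.1).** A patient in PR on day 8 would need about 56 − 49 = 7 days of hold to reach 56 days before ofatumumab. That is not a planned route, and time on hold is time off idelalisib.

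**The rates are descriptive.** No test or threshold depends on them. That limits the weight of the point but does not remove the misfit.

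**Conclusion.** The point holds for the idelalisib-alone ORR and CR rate. On the planned schedule without holds, no CR or PR can meet the section 10 duration before ofatumumab: 49 days are available at most, 55 with windows, against 56 or more. These rates therefore cannot be computed under the stated definitions without either scoring no responders or using persistence observed on combination therapy.

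The conclusion assumes that 2 months means at least 8 weeks, that the section 10 definitions govern the lead-in because nothing exempts it, and that the schedule runs unheld. The plan writes exceptions where it wants them, such as the lymphocytosis rules in section 10 and the four-month evaluation for the stage decision in section 14.1, so an unwritten one should not be presumed.

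A reader might go further and infer that the single-agent ORR will be reported as zero, or that the primary result is compromised. The documents support neither. Sections 1.1 and 8.2.3 suggest that a day-50 call was intended. The primary ORR belongs to the combination and its two-stage design is not clearly affected. Nodal PR with lymphocytosis states no duration of its own and is not clearly affected either. This is a should-fix point about descriptive secondary rates.

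**What to change.** Add one sentence to sections 10.1 and 14.2:

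> For the idelalisib-alone ORR and CR rate, response is scored at the cycle 2 day 22 restaging as a single time point, without the 2-month persistence requirement, and is reported as unconfirmed.

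This needs no new visit, test or sample. The cost is that these rates become less comparable with confirmed response rates, so the unconfirmed label should accompany them wherever they are reported.

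Do not also define 2 months as 56 days throughout section 10.1. That would alter the CR and PR definitions behind the primary ORR. It would also fail patients whose visits comply with the windows: restaging on day 53 and again on day 103 is allowed, but the two are only 50 days apart.

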10.1.3 Progressive disease

Progressive disease during or after therapy is characterized by at least one of the following:

- **Lymphadenopathy.** Progression of lymphadenopathy is often discovered by physical examination and should be recorded. In CLL, the use of CT scans usually does not add much information for the detection of progression or relapse. Therefore, the use of imaging methods to follow CLL progression is at the discretion of the treating physician.
- Disease progression occurs if one of the following events is observed: **(1)** Appearance of any new lesion, such as enlarged lymph nodes (>1.5 cm), splenomegaly, hepatomegaly, or other organ infiltrates. **(2)** An increase by 50% or more in greatest determined diameter of any previous site. **(3)** An increase in the previously noted enlargement of the liver or spleen by 50% or more or the de novo appearance of hepatomegaly or splenomegaly.

CONFIDENTIAL

This document is confidential. Do not disclose or use except as authorized.

- **Transformation to a more aggressive histology (eg, Richter syndrome). Whenever possible, this diagnosis should be established by lymph node biopsy.**
- **Occurrence of cytopenia (neutropenia, anemia, or thrombocytopenia) attributable to CLL.**

During therapy. Cytopenias may occur as a side effect of many therapies and should be assessed according to Appendix C.

After treatment. The progression of any cytopenia (unrelated to autoimmune cytopenia), as documented by a decrease of Hb levels by more than 20 g/L (2 g/dL) or to less than 100 g/L (10 g/dL), or by a decrease of platelet counts by more than 50% or to less than $100 \times 10^9/L$ (100 000/ μ L), which occurs at least 3 months after treatment, defines disease progression, if the marrow biopsy demonstrates an infiltrate of clonal CLL cells and there is no evidence for an autoimmune process.

